Outcome(s):	
The primary endpoint of this clinical trial is the incidence rate of postoperative hypersensitivity. The assessment of the postoperative hypersensitivity is performed and graded according to the FDI criteria (Hickel et al. 2007; Hickel et al. 2010, Hickel et al. 2022).
 
The secondary outcomes are the vitality and fracture rate of restored teeth and the retention/fracture rate of restorations. These parameters provide information about the clinical performance of the bond of the restoration to the tooth structure. Another secondary outcome is the marginal quality of the restorations that also provides information about the quality of the bond between tooth structure and luting composite. The secondary outcomes will be assessed at all recalls with the respective FDI criteria (Hickel et al. 2022).

Design:	
This is a prospective single-arm clinical investigation. The safety and performance results of ██████████ will be compared with the coded data of the control group (Adhese Universal) of an already performed clinical investigation ("Clinical evaluation of a new dual cure universal adhesive (Adhese Universal DC) in the indirect restorative therapy: A randomised, controlled clinical trial", NCT04475679). The study design of the planned clinical investigation follows the design of the previously conducted clinical investigation. The objectives, outcome parameters and methods are the same.

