3. CLINICAL INVESTIGATION OUTCOMES

3.1 Primary Outcome

Postoperative hypersensitivity is considered an indicator of the response of a tooth (pulp) to the therapeutic procedure applied. Postoperative hypersensitivity can be observed within a short time after the treatment. Therefore, it is assessed for the first time at the baseline recall (after 6-12days). The assessment of postoperative hypersensitivity includes questions about type and duration of pain, intensity of pain and on the stimulus inducing the pain (Hickel et al. 2007, Hickel et al. 2010, Hickel et al. 2022). The subjective perception of the intensity of postoperative hypersensitivity caused by thermal stimuli and caused by occlusal forces (during biting) will be determined by the aid of a Visual Analog Scale (VAS). The VAS values are brought into relationship to the preoperative values. In the table below a description of the correlation between FDI grade and VAS values and clinical signs and symptoms is shown. Not all signs need to be present at one stage. The exact VAS values vary widely from patient to patient, depending on each individual's pain tolerance. Therefore, it is one of the factors influencing the FDI grade, but it is not directly correlated. Not all the described conditions have to be fulfilled to attribute an FDI score. Depending on the intensity and character of the pain, further therapy will be determined. Usually, postoperative hypersensitivity subsides spontaneously, and no treatment is necessary. In case of very intense pain an immediate treatment is required. The application of a fluoride varnish is the first procedure of choice. If no improvement is achieved by this method, then the replacement of the restoration would be the next step. In the worst case, the pulp is severely inflamed, requiring endodontic treatment. If the postoperative hypersensitivity does not subside spontaneously or worsens after the applied treatment, the highest assessed FDI value is used for the statistical analysis.

For all participants a 1-month recall is planned to finally assess the postoperative hypersensitivity. The clinical experience of the evaluator is of major importance in the correct assessment of the FDI grade. In general, the rule applies, that in case of uncertainties the higher score is attributed.

FDI grade	1	2	3	4	5

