6. STATISTICAL METHODS

The trial is a continuation of the clinical trial "Clinical evaluation of a new dual cure universal adhesive (Adhese Universal DC) in the indirect restorative therapy: A randomised, controlled clinical trial (NCT04475679)". The methodology, the endpoints and the hypothesis are the same. The test product [REDACTED] is a further development of Adhese Universal DC. In the planned clinical investigation, the test group will be compared to the control group (Adhese Universal) of the study mentioned above. The statistical considerations of the already performed study are re-used and are therefore mentioned in the paragraphs below.

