6.1 Hypothesis

The null hypothesis is that there is a statistically significant difference between control and test group with respect to postoperative hypersensitivity.

The alternative hypothesis is that there is no difference between control and test group with regard to postoperative hypersensitivity.

We do not expect in this equivalence study to find any statistical significance between control and test group with regard to postoperative hypersensitivity.

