6.2 Determination of Sample Size

The number of samples estimated to be needed for each study arm is 40 to achieve the objective. The G*Power sample calculator software Version 3.1.9.2 was used to determine the sample size, at a power of 80% and a type I error of 0.1 (Faul et al., 2007; Faul et al., 2009).

Different to the previous study, this time a drop-out of 5 restorations is assumed. Therefore, the sample size aimed at is 45 instead of 40.

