6.4.2 Primary Analysis

Regarding the primary outcome, the interim analysis will be done at baseline. The final analysis of the primary outcome will be done after completion of the 1-month recall. The analysis will be done by the principal investigator within 3 months after the collection of the 1-month data.

A non-parametric test (Mann-Whitney) between two independent groups will be used to compare the level of postoperative hypersensitivity (FDI 11) between the control and the test group.

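### Section 6.1 declares an equivalence study with a difference as the null, but the only planned test has equality as its null and no margin or success rule is given, so no result can support the stated alternative

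*Combined protocol and SAP*

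**What the plan says.** Section 6.1 sets the hypotheses in equivalence order: "The null hypothesis is that there is a statistically significant difference between control and test group", with absence of a difference as the alternative. It names the design and the expected result: "We do not expect in this equivalence study to find any statistical significance between control and test group with regard to postoperative hypersensitivity".

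Section 6.4.2 gives the one inferential analysis: "A non-parametric test (Mann-Whitney) between two independent groups will be used to compare the level of postoperative hypersensitivity (FDI 11". It states no significance level. Section 6.4.3 makes the secondary analyses descriptive.

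Section 6.2 derives 40 teeth per arm "at a power of 80% and a type I error of 0.1" and adds 5 for drop-out. It names no test, effect size, margin or sidedness. Section 6 explains where this comes from: "The statistical considerations of the already performed study are re-used and are therefore mentioned in the paragraphs below".

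The endpoint is described in two ways. The synopsis (Outcomes) says "The primary endpoint of this clinical trial is the incidence rate of postoperative hypersensitivity", whereas 6.4.2 compares the level of FDI 11. On timing, section 3.1 says of hypersensitivity that "it is assessed for the first time at the baseline recall". Sections 3.1 and 4.1 put the final assessment at the 1-month recall. Section 3.1 also says that if hypersensitivity "does not subside spontaneously or worsens after the applied treatment, the highest assessed FDI value is used for the statistical analysis".

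**The concern.** An equivalence hypothesis is tested by rejecting the proposition that the groups differ by at least a stated amount. A Mann-Whitney test can only reject equality. The hypotheses in 6.1 and the test in 6.4.2 therefore point in opposite directions, and without a margin nothing connects them.

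The stated expectation of non-significance invites the reading that a non-significant p-value shows equivalence, although the plan does not say so outright. That reading rewards imprecision: the smaller the study, the easier it is to succeed. The synopsis calls this a pivotal study conducted for conformity assessment, so what is at stake is whether its only formal comparison with the control adhesive can support any conclusion of similarity.

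**Working it through.** **1. The logic.** Section 6.1 takes a difference as H0 and no difference as H1. Mann-Whitney takes equal distributions as H0.
- Significant result: equality is rejected, which agrees with the H0 of 6.1.
- Non-significant result: equality is not rejected, and the H0 of 6.1 has not been tested.

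Neither outcome rejects the H0 of 6.1. Its H1 is also exact equality, which no finite sample can establish. Moreover, statistical significance describes a sample result, so it cannot form part of a hypothesis about a population.

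**2. The plan's own figure.** The drop-out step is consistent: 40 + 5 = 45. The 40 itself cannot be reproduced, because the inputs are missing. Solving backwards at n = 40 per arm and 80% power (normal approximation, SD units):
- difference test, two-sided 0.1: (1.645 + 0.842) × √(2/40) = 0.556;
- difference test, one-sided 0.1: (1.282 + 0.842) × √(2/40) = 0.475;
- equivalence by two one-sided tests at 0.05 each, true difference zero: margin (1.645 + 1.282) × √(2/40) = 0.654.

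The same 40 fits three different problems, so 80% and 0.1 cannot be read as power and error rate for equivalence.

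**3. Reading non-significance as no difference.** Assumptions: a yes/no event, independent teeth, 45 test teeth, and 40 analysable control teeth (section 6.2 gives only the planned number). The incidences are assumed. The method is exact binomial enumeration over all outcomes, with the tie-corrected Mann-Whitney test and no continuity correction. Probability of a non-significant result:

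| True control vs test incidence | one-sided 0.1 | two-sided 0.1 | two-sided 0.05 |
|---|---|---|---|
| 5% vs 15% | 38% | 56% | 68% |
| 5% vs 20% | 18% | 33% | 44% |

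With 35 control teeth, the 5% vs 15% figure at two-sided 0.1 is 61%. Using three assumed five-grade distributions in place of a yes/no event gives 53% to 55% (40 vs 45). With only 10 teeth per arm, 5% vs 20% is non-significant 80% of the time, so shrinking the study raises the chance of apparent success.

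For contrast, take a rule that requires the Newcombe 90% confidence interval to lie inside ±15 points. With a true 5% vs 20%, a difference exactly at that margin, it wrongly declares equivalence 4.6% of the time (40 vs 45).

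**4. What one non-significant result looks like (hypothetical counts).** 2/40 vs 7/45 gives p = 0.12. The difference is 15.6% − 5.0% = 10.6 points, with a Newcombe 90% interval of −0.8 to +21.9. If 1 control and 4 test episodes had resolved by 1 month and were not counted, the same teeth give 1/40 vs 3/45: a difference of 4.2 points, interval −4.7 to +13.3. The event definition therefore has to come before the margin.

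**5. What this size can support.** Margin giving 80% power for the 90% interval to lie inside it, with equal true rates:

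| Incidence | 40 vs 45 teeth | 35 vs 45 teeth |
|---|---|---|
| 5% | ±16 | ±16 |
| 10% | ±20 | ±21 |
| 20% | ±25 | ±26 |

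Two teeth per patient widen these. The design effect is 1 + ICC × (Σm²/Σm − 1), where m is teeth per patient. The ICC is assumed to be 0.2, with the same pairing in the control group.
- 30 patients (15 pairs, 15 singles; an assumed mix): 1 + 0.2 × (75/45 − 1) = 1.133, effective 35 vs 40 teeth, margins about ±17, ±21 and ±27.
- 23 patients (22 pairs, 1 single; the minimum in section 4.1, hence maximum pairing): 1 + 0.2 × (89/45 − 1) = 1.196, effective 33 vs 38 teeth, margins about ±18, ±22 and ±28.

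**The case against.** - **A margin may exist in the earlier trial's plan.** That is possible and cannot be checked here. But section 6 says the re-used considerations appear in the paragraphs that follow, and no margin does. The finding is limited to this document.
- **Equivalence appears only in 6.1, and the primary objective is to determine a rate and compare it.** The descriptive estimate of the test-group rate is indeed unaffected. The comparison is still part of the primary objective, and 6.1 is the only statement of what it should show.
- **A rank test on an ordinal grade is legitimate and needs no event threshold.** True as a test of difference. It does not yield the incidence named as the endpoint, and an ordinal equivalence analysis would also need a margin.
- **Section 6.4.2 fixes the final primary analysis after the 1-month recall.** It does, and that narrows the timing gap to one question: does an episode that has resolved by then count? The natural reading may be that it does not, but the rule in 3.1 covers only episodes that persist or worsen.
- **The illustrative figures depend on an unstated level and sidedness.** This stands. The 5% vs 15% figure ranges from 38% to 68%, and the counts, incidences and ICC are assumptions. The logical defect depends on none of them.
- **Section 6.3 has stopping rules.** They are partial safeguards. If applied to 45 teeth (6.3 gives no denominator for the first), they need at least 6 teeth above grade 3 on FDI 11 (6/45 = 13.3%) before baseline, or at least 10 restorations at grade 5 on any criterion (10/45 = 22.2%). Neither compares with control.

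**Conclusion.** The concern holds and must be fixed. Carried out exactly as written, the plan cannot reject its own null hypothesis or support an equivalence statement. This follows from setting 6.1 beside 6.4.2 and needs no outside figure.

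The practical size rests on the stated assumptions. A threefold true incidence (5% vs 15%) would go undetected in roughly four to seven of ten such studies, depending on the test level. A sound equivalence analysis at 40 to 45 teeth has 80% power only for margins of about ±16 to ±25 points, and wider ones if teeth within a patient are correlated. Whether such margins are clinically defensible is not something the documents answer.

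**What to change.** 1. Designate which FDI 11 grades count as a hypersensitivity event. State whether incidence is cumulative (any event from the baseline recall to the 1-month recall) or means present at 1 month. Apply the same definition to the control data.
2. In 6.1, state H0: |difference| ≥ Δ and H1: |difference| < Δ. Justify Δ clinically, fix it before test data are compared with control, and disclose whether the control results were known when it was set. If the earlier plan holds a margin, state it here with its justification.
3. In 6.4.2, make the primary comparison the incidence difference with a two-sided 90% confidence interval that allows for two teeth per patient, or use a margin-based ordinal analysis. Claim equivalence only if the whole interval lies within ±Δ. Mann-Whitney can stay as supportive.
4. In 6.2, replace the bare power and error statement with the power that 40 to 45 teeth give for that Δ. State the assumed incidence, the analysable control teeth and the within-patient correlation.
5. If no clinically justified Δ is supportable at this size, remove the equivalence wording and the sentence expecting non-significance, and report the estimated difference with its interval.

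The cost is rewording 6.1, 6.2 and 6.4.2 plus one event definition, with no extra teeth or visits. The price is that equivalence becomes harder to claim, the stated power looks less favourable, and the sponsor may have to give up the equivalence claim.

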6.2 Determination of Sample Size

The number of samples estimated to be needed for each study arm is 40 to achieve the objective. The G*Power sample calculator software Version 3.1.9.2 was used to determine the sample size, at a power of 80% and a type I error of 0.1 (Faul et al., 2007; Faul et al., 2009).

Different to the previous study, this time a drop-out of 5 restorations is assumed. Therefore, the sample size aimed at is 45 instead of 40.

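### The 80% power at type I error 0.1 in Section 6.2 rests on no stated effect size, rate, margin or sidedness and matches neither the equivalence aim nor the planned Mann-Whitney test

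*Combined protocol and SAP*

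**What the plan says.** Section 6 presents the study as a continuation of a randomised trial whose control group serves as an external comparator: "The statistical considerations of the already performed study are re-used".

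Section 6.1 takes a difference as the null hypothesis and no difference as the alternative. It gives no margin and adds: "We do not expect in this equivalence study to find any statistical significance between control and test group".

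Section 6.2 states: "The number of samples estimated to be needed for each study arm is 40 to achieve the objective". The basis is a G*Power run "at a power of 80% and a type I error of 0.1". The software version is named, but not the test family, sidedness, effect size, expected rate or standard deviation. The one change for this study is that "this time a drop-out of 5 restorations is assumed", which takes 40 to 45.

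Section 6.4.2 plans a Mann-Whitney comparison of the FDI hypersensitivity grade between test and control. It names no significance level, no equivalence test and no confidence interval set against a margin.

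**The concern.** Power is the probability of reaching a stated conclusion under a stated truth. Section 6.2 ties 80% to achieving the objective, and Section 6.1 makes that objective a finding of no difference. The planned test can only find a difference or fail to find one. As the power of that test, 80% would be the chance of the outcome the sponsor does not expect, for a difference of unknown size.

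This is a pivotal study for conformity assessment, with hypersensitivity as the primary endpoint. A non-significant p-value is likely to be read as equivalence backed by 80% power. The documents give that reading no basis. The earlier calculation also treated both arms as unknown, whereas here the control results already exist and are not used.

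**Working it through.** **Inputs.** From Section 6.2: 40 per arm, power 80%, type I error 0.1, and 5 drop-outs. The control group's actual size is not given, so 40 is used. Rates of 5%, 10% and 20% are assumptions. Teeth are treated as independent. Normal quantiles: z(0.80) = 0.842, z(0.90) = 1.282, z(0.95) = 1.645.

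**1. The plan's own figure.** The drop-out step is consistent: 40 + 5 = 45. The 40 cannot be recomputed, because every sample-size formula needs an effect size. It can only be back-solved, as d = (z + 0.842) × √(2/40):
- one-sided 0.1: (1.282 + 0.842) × 0.2236 = 0.47 SD
- two-sided 0.1: (1.645 + 0.842) × 0.2236 = 0.56 SD

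Dividing by √0.955 for Mann-Whitney efficiency gives 0.49 and 0.57. An assumed d of 0.5, one-sided, needs 37 per arm (t-test) or 39 (Mann-Whitney), close to 40. That d is not in the documents, and this would still be power to find a difference.

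**2. Can 40 follow from the expected outcome?** The chance of a non-significant result when both groups have a 10% rate (pooled z-test, two-sided 0.1, exact binomial enumeration):

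| Teeth per arm | Non-significant |
|---|---|
| 40 | 89% |
| 20 | 90% |
| 10 | 95% |

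The nominal value is 1 − 0.1 = 90% at any size; the 95% at 10 per arm comes from the discreteness of small counts. Fewer teeth do as well or better, so this criterion does not lead to 40.

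**3. What 40 v 40 can detect.** Power = Φ{[(p2 − p1) − 1.645·S0]/S1}, where p̄ is the mean of p1 and p2, S0 = √(2p̄(1 − p̄)/40) and S1 = √{[p1(1 − p1) + p2(1 − p2)]/40}. For 10% v 32.4%: S0 = 0.0914, S1 = 0.0879, and (0.224 − 0.150)/0.0879 = 0.84, so power is 80%. The doubling columns are exact enumerations of the same test.

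| Assumed control rate | Test rate for 80% power (two-sided 0.1) | Power for a doubling, two-sided 0.1 | Same, one-sided 0.1 |
|---|---|---|---|
| 5% | about 24% | 24% | 35% |
| 10% | about 32% | 35% | 49% |
| 20% | about 46% | 64% | 75% |

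A simulated Mann-Whitney test on an assumed grade distribution of 90/6/2/1/1% also missed the doubling from 10% about 65% of the time at two-sided 0.1.

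**4. What an equivalence test would need.** For two one-sided tests with true difference zero, power = 2Φ(m/SE − z) − 1, with SE = √(2p(1 − p)/40). Setting this to 80% gives m = (z + 1.282) × SE, which is 2.563 × SE at 0.1 per side.

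| Assumed common rate | SE | Margin for 80% power, 0.1 per side | Power at a 10-point margin |
|---|---|---|---|
| 5% | 0.0487 | 12.5 points | 56% |
| 10% | 0.0671 | 17.2 points | 17% |
| 20% | 0.0894 | 22.9 points | 0% |

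At 0.05 per side the margins become 14.3, 19.6 and 26.2 points. At an assumed rate of 2%, SE = 0.0313 and the margin at 0.1 per side is 8.0 points by this formula. An exact calculation with Newcombe limits gives about 78% power at 10 points, so the range there is about 8 to 10 points.

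**The case against.** The best defence is that the original G*Power run is not visible. It may have had a proper effect size, and some margin always gives 80% power. That stands. The supportable statement is that 80% cannot be reproduced or tied to Sections 6.1 and 6.4.2. It has not been shown to be miscalculated, and the step from 40 to 45 is correct.

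Three stronger readings are tempting:

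- **The design would usually miss a doubling of hypersensitivity.** This holds from assumed rates of 5% or 10% at two-sided 0.1, but not from 20%, where power is 64%. A one-sided test, which Section 6.2 does not exclude, does better still. The documents give no control rate to choose between these.
- **Only very wide margins are reachable.** Width depends on the assumed rate: 12.5 points at 5%, and roughly 8 to 10 points at 2%. The documents contain no clinical benchmark for what is too wide.
- **The analysis will be run at 0.05, so the real power is lower.** No such level appears. The 0.1 in Section 6.2 is the only one given, and its absence from Section 6.4.2 is a gap in clarity, not a contradiction.

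It may also be said that the root problem is an equivalence claim without a margin. That is a wider matter; the power sentence needs correcting even if the claim is reworded.

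**Conclusion.** The point holds as a mismatch between the stated power and the stated objective and test, together with missing inputs. The 80% gives no support to reading a non-significant result as equivalence. On the assumed rates of 5%, 10% and 20%, 40 v 40 has 80% power only for rises of about 19, 22 and 26 percentage points (24 − 5, 32 − 10, 46 − 20) at two-sided 0.1. Equivalence at 0.1 per side would need margins of about 12.5, 17 and 23 points.

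These sizes rest on the assumed rates, on 40 control teeth and on independence. Section 4.1 allows as few as 23 patients for 45 teeth; positive correlation between two teeth in one mouth would lower the effective number and widen every figure. The lack of inputs and the mismatch do not depend on any assumed rate. The matter should be corrected, but it does not call for more teeth.

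**What to change.** Keep 45 teeth and rewrite the power paragraph in Section 6.2:

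1. Remove the claim that 80% power supports the equivalence objective.
2. Using the actual control number and observed control grades, state the difference that 40 test teeth can detect at 80% power with the planned test, and the expected confidence-interval width for the difference in incidence. Allow for two teeth per participant, and say which grades count as a case, since the documents do not define this.
3. Say that a non-significant result cannot rule out differences smaller than the detectable one.
4. State the same significance level and sidedness in Sections 6.2 and 6.4.2.

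Any equivalence margin needs its own clinical justification. The detectable difference, or a margin solved from 40 teeth as in the working above, must not be adopted as the criterion.

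The cost is one recalculation from data the sponsor already holds and a short text change, with no added patients. The downside is that the stated figure will look less favourable.
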